7.2.6 Subgroup analysis

It is not intended to do any subgroup analysis.

7.3. Clinical and anthropometric secondary outcome analysis

As for the primary outcome, the analysis of each continuous secondary outcome measured across the study timepoints will be compared between arms at 12-months using a linear mixed effects model adjusting for all minimisation factors, age (continuous) and, where collected, the baseline of the outcome and the associated missing indicator (if there is missing data in the baseline of outcome). *Time* will be represented as categorical contrasts in main effect form and in interaction with all other fixed effects.

To assess the arm effect on the study population 'during' the 12 months, the area under the curve of the estimated between-group intervention effects at 2, 6 and 12 months (where appropriate) will be estimated as well as the respective standard errors and covariances. This is possible because the intervention effect parameters from the linear mixed effects model have a population average interpretation as well as subject-specific. This will be supported by estimating cross-sectional differences between arms at these timepoints.

Where possible, study analyses will be used to provide estimates and two-sided 95% confidence intervals. For the secondary endpoints presented in section 3.9 of the protocol, the following methods of analyses are planned:

Objectives		Variables	Main summary statistic	Statistical method for comparison between arms and inference type
2.	To determine effects on glucose homeostasis as a surrogate marker of type-2 diabetes risk	Fasting biochemistry:Glucose (mmol/L)Insulin (mIU/L)	Means(SE)	LME incorporating the 2, 6 and 12-month timepoints described with 95% Confidence intervals.
3.	To determine effects on blood lipid and cholesterol as surrogate markers of CVD risk	 Fasting biochemistry: Triglycerides (mmol/L) Total cholesterol (mmol/L) LDL cholesterol (mmol/L) HDL cholesterol (mmol/L) 	Means(SE)	LME incorporating the 6 and 12-month timepoints described with 95% Confidence intervals.
4.	To determine effects on blood pressure as a surrogate marker of CVD and stroke risk	Blood pressure: - SBP (mm/Hg) - DBP (mm/Hg)	Means(SE)	LME incorporating the 2, 6 and 12-month timepoints described with 95% Confidence intervals.

iPRFV/FNT

	Objectives	Variables	Main summary statistic	Statistical method for comparison between arms and inference type
5.	To compare changes in body weight/ waist/ BMI/body composition during the 12 months intervention	 Body weight Waist/hip BMI (kg/m²) Body composition: Fat mass (FM) (kg) Fat Mass Index (FMI) (kg/m²) Percent body fat (Fat%) Fat free body mass (FFM) (kg) FM/FFM ratio 	Means(SE)	LME incorporating the 2, 6 and 12-month timepoints described with 95% Confidence intervals.

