4.6. Schedule of Time and Events

A full schedule on the timing of measures is provided in below (as in section 6.5 of protocol). The plus or minus sign are a target/guide for when the visits should happen. If any fall below/above these, the closest measurement to the visit will be used.

Assessment	Screening	Baseline/ Randomisation (1-4 weeks after screening)	2 months (+/- 2 week)	6 months (+/- 4 weeks)	12 months (+/- 4 weeks)
Consent	X				
Demographics	X				
Randomisation		Х			
Medical History	X	Х	X	Х	Х
Concomitant medications	X	Х	Х	Х	Х
Pregnancy test - females only	X	Х	X	Х	Х
Electrocardiogram (ECG)	X				
Vital signs: DBP, SBP and HR	X	X	X	Х	Х
Trial intervention		Х	X	Х	
Height, body weight, waist/hip measurements, BMI, body composition	X	Х	Х	Х	Х
Fasting blood test (glucose, insulin, lipid profile)		Х		Х	Х
Full Blood Count & Vitamin B12	X				
Food diary		Х	X	Х	Х
IPAQ	X	Х	X	X	Х
Lifestyle questions	X	X	X	X	X
Sachet count (compliance)			X	X	X
Adverse event tracking		X	X	X	X

Mechanistic evaluation

(52 ppts; Imperial site only)

(c= ppis, imperial site only)			n	•	i
Assessment	Scree ning	Baseline/Randomisation (1-4 weeks after screening)	2 months (+/- 2 week)	6 months (+/- 4 weeks)	12 months (+/- 4 weeks)
Energy expenditure (indirect calorimetry)		Х			Х
Appetite regulation (VAS, food diary, ad libitum test meal, and blood tests for anorectic gut hormones)		Х			Х
Substrate oxidation/DNL (via stable isotype tracers in water consumption) – ¹³ C breath, urine and blood samples		Х			Х
Gut microbiota (stool sample and hydrogen breath test)		Х			Х
Neuroendocrine cell number (stool sample)		X			X
Accelerometry		Х			Х

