6.2. Clinical and anthropometric outcome variables

The secondary outcome measures are listed as follows according to the type of the variable (continuous, categorical) and the sample (full sample, mechanistic sub-sample). Each will be analysed at the 12-month principal timepoint of follow-up but may also be presented at earlier follow-up timepoints (2 and 6 months)

for the purpose of secondary analysis. These will be listed at a later point when justifying the analysis method to be used.

Sec	condary objectives	Variables (all in full sample)	Type of variable	Timepoint(s) of evaluation of endpoint
1.	To determine effects on glucose homeostasis as a surrogate marker of type-2 diabetes risk	Fasting biochemistry: -Glucose (mmol/L) -Insulin (mIU/L)	Continuous	6 and 12 months
2.	To determine effects on blood lipid and cholesterol as surrogate markers of CVD risk)	 Fasting biochemistry: Triglycerides (mmol/L) Total cholesterol (mmol/L) LDL cholesterol (mmol/L) HDL cholesterol (mmol/L) 	Continuous	6 and 12 months
3.	To determine effects on blood pressure as a surrogate marker of CVD and stroke risk	Blood pressure (mean of 3 measurements each): - SBP (mm/Hg) - DBP (mm/Hg)	Continuous	2, 6 and 12 months
4.	To compare changes in body weight/ waist/ BMI/body composition during the 12 months intervention	 Body weight Waist/hip BMI (kg/m²) Body composition: Fat mass/Total body fat (FM) (kg) Fat Mass Index (FMI) (kg/m²) Percent body fat (Fat%) (taken from Body Impedance machine) Fat free body mass (FFM) (kg) FM/FFM ratio 	Continuous	2, 6 and 12* months

* Body weight already included as primary outcome at 12 months

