7.2. Primary outcome analysis

7.2.1 Description

be included.

The primary outcome measure is the change from baseline in body weight at 12 months. As the analysis approach for continuous outcomes below makes advantage of linear covariate-adjustment for the baseline of the outcome, the primary endpoint can equivalently be regarded to be each participant's 12-month measurement. This is convenient because then those with a 12- month outcome, but whose baseline measurement is missing, are not regarded to be missing the endpoint. The primary outcome is therefore operationalised within the statistical model as the 12-month body weight, rather than the change in this from baseline to 12 months. It is not thought that this outcome will be missing at baseline, as it is involved in eligibility criteria and is a minimisation factor. This approach may be more useful for other outcomes. The primary outcome will be analysed using a repeated measures ANCOVA via a linear mixed effects (LME) model incorporating the 3 post-baseline measurements of the body weight (2, 6 and 12 months). All outcome measurement from all randomised subjects who provide at least one post-baseline valid measurement will

This mixed model will include fixed effect terms for arm (1 parameter), centre (1 parameter), sex (1 parameter), age (1 linear parameter), BMI within ethnicity (3 parameters), whether or not subjects volunteer to take part in the sub study (1 parameter), "time" (2 parameters), the baseline of the outcome (continuous body weight -1 parameter) and its missing indicator required for the missing indicator method (1 parameter , if needed) (20). Additionally, the model will include a fixed effect to indicate whether the primary outcome was measured by the participant at each timepoint. The other effects to be included in the model will be the interactions between "time" and each of the other fixed effects in the model (20 parameters). This model allows the treatment effect to be formally tested, at the primary timepoint of 12 months, and estimated at 2 and 6 months. Age is included because this was found to predict drop-out in a related trial (21).

Models will be fitted using a restricted maximum likelihood estimation using an unstructured variancecovariance matrix for the within-subject residuals (since there are only three follow-up timepoints, and so there is a manageable enough number of covariance parameters to expect this type of matrix to be supported by the sample size).

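### Blood pressure, waist/hip and body composition are measured at both screening and baseline, but the secondary models adjust for only one of the two values, which gives up some precision

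*SAP*

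**What the plan says.** The visit schedule (SAP 4.6) has one row for "Vital signs: DBP, SBP and HR" and one for "Height, body weight, waist/hip measurements, BMI, body composition". Both rows are marked at screening and at baseline/randomisation, with 1 to 4 weeks between the visits. The flow diagram in 7.1.5 puts both visits before allocation. The fasting blood test is marked at baseline but not at screening.

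For the secondary outcomes, 7.3 plans a mixed model "adjusting for all minimisation factors, age (continuous) and, where collected, the baseline of the outcome and the associated missing indicator", the indicator being used only if baseline values are missing. The primary model in 7.2.1 likewise carries one term for "the baseline of the outcome (continuous body weight -1 parameter) and its missing indicator required for the missing indicator method". For weight, the SAP adds: "It is not thought that this outcome will be missing at baseline, as it is involved in eligibility criteria and is a minimisation factor".

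Nowhere does the SAP use the screening value as a covariate, in an average or in place of a missing baseline. It also never says which of the two readings is the baseline, although the baseline visit is the natural reading.

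**The concern.** A single pre-treatment reading contains visit-to-visit noise, and that noise weakens it as a covariate. A second reading of the same quantity, also taken before allocation, would recover part of the loss without new data. The SAP presents the secondary outcomes through effect sizes with 95% confidence intervals (sections 6 and 7.10), so what is at stake is the width of those intervals. In addition, when a baseline reading is missing, 7.3 falls back on an indicator although a screening reading from the same person should usually be available.

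**Working it through.** **The plan's own figure.** Inputs from SAP 4.5: difference 2 kg, SD 4.35 kg, two-sided 5%, power 90%, 25% loss. The t-based sample size is 100.4 per arm, rounded up to 101. Then 101/0.75 = 134.7, rounded up to 135 per arm, or 270 in total. Power at 101 per arm is 90.4% (normal approximation). The stated size reproduces and does not depend on a second pre-treatment value.

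**Blood pressure, by correlations.** Let ρ be the correlation of a pre-treatment reading with the 12-month reading (the same for both pre-treatment readings), and r that between screening and baseline. As fractions of the total variance, the residual variance is
- with one reading: 1 − ρ²
- with two readings: 1 − 2ρ²/(1 + r)

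The SAP gives neither correlation, so these values are assumptions:

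| ρ | r | one | two | variance reduction | CI narrower by |
|---|---|---|---|---|---|
| 0.5 | 0.8 | 0.750 | 0.722 | 3.7% | 1.9% |
| 0.5 | 0.7 | 0.750 | 0.706 | 5.9% | 3.0% |
| 0.6 | 0.8 | 0.640 | 0.600 | 6.2% | 3.2% |
| 0.6 | 0.7 | 0.640 | 0.576 | 9.9% | 5.1% |
| 0.6 | 0.6 | 0.640 | 0.550 | 14.1% | 7.3% |

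**Blood pressure, by variance components.** Let Vb be the between-person variance, Vw the visit-to-visit variance, Vc the variance of true 12-month change, and Vf = Vb + Vw + Vc. The residual variance is
- with one reading: Vf − Vb²/(Vb + Vw)
- with two readings: Vf − Vb²/(Vb + Vw/2)

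Example for systolic pressure with assumed SDs of 11 (between), 6 (visit) and 5 (change) mmHg: Vf = 121 + 36 + 25 = 182.
- One reading: 182 − 14641/157 = 88.7
- Two readings: 182 − 14641/139 = 76.7
- Reduction: 13.6%

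Varying the assumptions, with between-person SD 11 and visit SD 4 to 8 for systolic, and 8 and 3 to 6 for diastolic:

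| SD of true change | systolic | diastolic |
|---|---|---|
| 8 | 7.0% to 9.7% | 4.6% to 7.3% |
| 5 | 12.0% to 13.6% | 8.8% to 11.0% |
| 0 | 15.6% to 22.0% | 15.2% to 21.8% |

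The 22% corner needs no true change in a year and a visit SD of 4. That implies a baseline-to-12-month correlation of 121/137 = 0.88.

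**Waist.** With assumed SDs of 8 cm (between), 1.5 to 2.5 cm (visit) and 4 cm (change), the same formulas give 5.2% to 9.7%. For body composition there is no basis for a figure.

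**Body weight.** Averaging two readings lowers the variance of change by s²/2, where s is the short-term within-person SD (assumed). The plan's variance is 4.35² = 18.92.
- s = 0.5 kg: 0.125/18.92 = 0.7%, power 90.4% to 90.6%
- s = 0.7 kg: 0.245/18.92 = 1.3%, power to 90.8%
- s = 1.0 kg: 0.5/18.92 = 2.6%, power to 91.2%

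**The case against.** Adjusting for one prespecified baseline is standard and gives an unbiased comparison of the arms. The SAP contradicts nothing here. That stands in full: this is an efficiency improvement, not the correction of an error.

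The gain is unknown because the SAP has no repeatability data, and other covariates already absorb some between-person variance. That also stands, so the SDs above are best read as what remains after adjustment, and the result is given as a range. Blood pressure is moreover already averaged within a visit ("Blood pressure (mean of 3 measurements each"). Averaging reduces error within a visit but not variation between visits, which is the part a second visit addresses.

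The consequences are small: the only p-value promised in section 6 is for the primary test. Section 8.2 also warns that the model may have too many parameters. Both points argue for keeping the change out of the primary model and giving the extra term a low rank in the secondary ones.

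A reader might infer that every model is affected, that the primary comparison is materially weaker than it could be, or that the loss equals a quarter more participants. The documents support none of these. Glucose, insulin and lipids have no screening value. For weight the gain is under one point of power. The large figure appears only in the corner with no true change.

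A reader might also infer that missing baselines are a serious problem. The indicator is used only if needed, and baseline weight is not expected to be missing.

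**Conclusion.** The point holds as a modest, cheap gain for blood pressure, waist/hip and body composition in 7.3. Under the assumed correlations and SDs, residual variance falls by roughly 4% to 14% for systolic and diastolic pressure and about 5% to 10% for waist; body composition cannot be quantified. For body weight the 0.7% to 2.6% gain does not justify a nearly collinear term in the primary model. At a given height BMI is weight rescaled, so the same applies to it. The present analysis remains valid and unbiased, and the sample size is unaffected.

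**What to change.** In 7.3, for systolic and diastolic pressure, waist/hip and body composition:
- define baseline as the value from the baseline visit;
- add the screening value as a second continuous covariate, with its interaction with time;
- keep the missing indicator for the baseline value. The screening covariate then still carries information when the baseline reading is absent.

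Entering the two values separately makes no assumption that their means are equal.

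In 7.2.1, add only that the screening weight is used if the baseline weight is missing.

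The cost is three parameters per secondary model (one main effect and two time interactions) and a sentence in each section. No new data are needed. Because 8.2 foresees non-convergence, state there that the screening terms are the first to be dropped.

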7.4. Lifestyle factors analysis

Lifestyle factors will be summarized over time using simple descriptive statistics.

Objectives	Variables	Main summary statistic	Statistical method for comparison between arms and inference type†
A. To compare changes in physical activity during the 12 months intervention	IPAQ (ordered) categorical score (all patients) -Low -Moderate -High	Unadjusted patient proportions at 2, 6 and 12months and change from baseline Cross-tabulations of the ordered categorical IPAQ with baseline	Linear-by-linear association test at 12 months
	Accelerometer data (for sub study participants only): - total energy expenditure (KJ) - active energy expenditure (KJ) - average metabolic equivalent of tasks (METs) - physical activity duration - step count - duration on body - lying down - sleep duration	Means (SD) / Medians (IQR) Mean and SD of change in accelerometry from baseline	95% CI for difference analogous to a T-test
B. To compare changes in other lifestyle factors during the 12 months intervention	 Smoking status (current/ex- smoker/never) Vaping status (current/ex- vaper/never) Drinking status (current/ex- drinker/never) Recreational substances status (yes/no) 	Unadjusted patient proportions at 2, 6 and 12months and change from baseline Cross-tabulations with baseline	95% CI for difference in current status analogous to a chi- squared test
C. To compare changes in diet during the 12 months intervention	Food diaries: -Energy (in kcal or kJ) -Protein (g) -Fat (g) -Carbohydrate (g) -Fibre (g)	Means(SD)/ Medians(IQR) Mean and SD of change from baseline	95% CI for difference analogous to a T-test

*Differences in these lifestyle factors between arms would lead to sensitivity analyses.

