3.6. Changes in lifestyle factors

Some of the following lifestyle factors can alter weight (e.g. quitting or taking up smoking, or a marked change in physical activity), but would not be thought to have arisen from the intervention.

- 1. To compare changes in physical activity during the 12-month intervention.
- 2. To compare changes in other lifestyle factors during the 12-month intervention; smoking, drinking and recreational drugs.
- 3. To compare changes in diet during the 12-month intervention (via food diaries).

Notes:

Physical activity: Measure of level and time spent on activities by a person, according to the IPAQ Smoking: Cigarettes, cigars or vaping

Drinking: Alcoholic drinks of any type

Recreational drugs: Legal and illegal drugs taken for recreational purposes in any form

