6. ANALYSIS VARIABLES

Many of the study variables are measured at more than one visit (section 4.6 above). In the reporting of the analysis the latest timepoint will be taken to be most important. Usually this will be at 12 months.

The trial is powered on the outcome measure of body weight at 12 months. A p-value will be provided for this hypothesis test. For this and other outcomes 95% confidence intervals will be presented.

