6.3. Lifestyle factors' variables

Lifestyle factors	Variables	Type of variable	Timepoint(s) of evaluation of endpoint
A. To compare changes in physical activity during the 12 months intervention	IPAQ (International Physical Activity Questionnaire) scores (all participants) - Low - Moderate - High	Categorical	2, 6 and 12 months
	Accelerometer data (Sub-study participants only): - total energy expenditure - active energy expenditure - average metabolic equivalent of tasks (METs) - physical activity duration - step count - duration on body - lying down - sleep duration	Continuous	Baseline and 12 months

	Lifestyle factors	Variables	Type of variable	Timepoint(s) of evaluation of endpoint
B.	To compare changes in other lifestyle factors during the 12 months intervention	 Smoking status (current/ex-smoker/never) Vaping status (current/ex-vaper/never) Drinking status (current/ex-drinker/never) Recreational substances status (yes/no) 	Categorical	2, 6 and 12 months
C.	To compare changes in diet during the 12 month intervention	Food diaries: -Energy (in kcal or kJ) -Protein (g) -Fat (g) -Carbohydrate (g) -Fibre (g)	Continuous	2, 6 and 12 months

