7.1.2 Outcomes requiring derivation

The International physical activity questionnaire (IPAQ) short form asks about three types of activity undertaken in four domains: a) leisure time physical activity, b) domestic and gardening activities, c) work-related physical activity and d) transport-related physical activity. It provides separate scores on walking,

moderate-intensity and vigorous-intensity activity which are summarized using median and interquartile range values and expressed in MET-minutes/week (17). According to the IPAQ guideline, "METs are multiples of the resting metabolic rate and a MET-minute is computed by multiplying the MET score of an activity by the minutes performed". A combined total physical activity score is also reported and calculated from the summation of the duration in minutes and frequency (days) of walking, moderate-intensity and vigorous-intensity activities. In the current study, the categorical variable of IPAQ will be used, which describe the physical activity in three levels: Low, Moderate and High. The data cleaning and processing (including missing value guidance) of IPAQ will be followed according to the guideline(17).

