7.10. Handling multiple comparisons

Significance tests will be used sparingly and restricted where possible to addressing stated hypotheses. Secondary outcomes, as well as the primary outcome, will be summarised using an effect size with a 95% confidence interval. Interpretation for those secondary outcomes that do not directly address the stated study hypotheses will be more cautious. Where multiple outcomes address an objective, the interpretation will account for the role of the outcome within the objective and the strength and direction of effects in all outcomes.

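### IPAQ physical activity is compared between arms only by a 12-month test that ignores baseline and gives no effect estimate or 95% CI, unlike every other row of SAP table 7.4

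*SAP*

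**What the plan says.** - **Objective.** SAP section 3.6 states it as "To compare changes in physical activity during the 12-month intervention", and the table in section 6.3 repeats it.
- **Variable.** Section 7.1.2: "In the current study, the categorical variable of IPAQ will be used". The levels are Low, Moderate and High, recorded at 2, 6 and 12 months.
- **General reporting rule.** Section 6 says of the primary test: "A p-value will be provided for this hypothesis test". It continues: "For this and other outcomes 95% confidence intervals will be presented".
- **Multiplicity section.** Section 7.10: "Significance tests will be used sparingly and restricted where possible to addressing stated hypotheses". It adds: "Secondary outcomes, as well as the primary outcome, will be summarised using an effect size with a 95% confidence interval".
- **IPAQ row of table 7.4, summary column.** Unadjusted proportions at each follow-up visit, change from baseline, and cross-tabulations against baseline category.
- **IPAQ row of table 7.4, between-arm column.** "Linear-by-linear association test at 12 months", and nothing else.
- **Other rows of table 7.4.** Accelerometry (sub-study participants only), the smoking, vaping, drinking and drug items, and the food diaries each have a 95% CI for a difference.
- **Note to table 7.4.** Differences between arms in these factors would lead to sensitivity analyses.

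**The concern.** A linear-by-linear test produces a statistic and a p-value. It does not say how far apart the arms are or what range of differences the data allow. Table 7.4 names no accompanying estimate, so the IPAQ row departs from the section 6 commitment and from the rest of its own table. It is also a significance test on a variable for which section 3.3 states no hypothesis, which sits badly with section 7.10.

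The test uses 12-month categories alone, whereas the objective concerns change. Baseline IPAQ is collected and tabulated but does not enter the between-arm inference.

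What is at stake is the reading of the weight result. Section 3.6 names a marked change in physical activity as something that can alter weight, and the note to table 7.4 makes an arm difference the reason for further analyses. A non-significant p-value cannot show that an important imbalance has been excluded. A significant one carries no interval and no allowance for baseline.

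**Working it through.** The SAP gives no figure for this comparison, so there is none to reproduce. The check sets the sections side by side and then illustrates the consequence.

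**Side by side**

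| Table 7.4 entry | Measured in | Between-arm method | 95% CI named? |
|---|---|---|---|
| IPAQ category | all participants | linear-by-linear test, 12 months | no |
| Accelerometry | sub-study only | difference, as for a t-test | yes |
| Smoking, vaping, drinking, drugs | all participants | difference in current status | yes |
| Food diaries | all participants | difference, as for a t-test | yes |

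**Illustration.** The SAP gives no IPAQ rates, so all counts are assumed. The arm size of 101 is the expected 12-month follow-up in the section 7.1.5 flow diagram. Scores are Low = 1, Moderate = 2, High = 3.

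Assumed 12-month counts (Low/Moderate/High): inulin 40/40/21, IPE 30/41/30.

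1. *Planned test.* M² = (N − 1)r² on 1 df.
   - Mean scores are 183/101 = 1.812 (inulin) and 202/101 = 2.000 (IPE), a difference of 0.188.
   - Total sum of squares = 853 − 385²/202 = 119.21.
   - Between-arm sum of squares = 50.5 × 0.188² = 1.787, using the unrounded difference 19/101.
   - r² = 1.787/119.21 = 0.01499, so M² = 201 × 0.01499 = 3.01 and p = 0.083.
2. *Difference in proportion Low, same data.*
   - 30/101 − 40/101 = −9.9 percentage points.
   - SE = √(0.396 × 0.604/101 + 0.297 × 0.703/101) = 0.0666.
   - 95% CI = −9.9 ± 1.96 × 6.66 = −23.0 to 3.2 points.
3. *Proportional odds model, arm only, same data.*
   - Log odds ratio 0.455, SE 0.262.
   - Odds ratio for a higher category with IPE = 1.58 (95% CI 0.94 to 2.63).
4. *Role of baseline.* Keep the same 12-month counts.
   - Baseline 50/36/15 in both arms (mean 167/101 = 1.653): mean-score change is 16/101 = 0.158 (inulin) and 35/101 = 0.347 (IPE), so the arms differ in change by 0.19.
   - Baseline 50/36/15 (inulin) and 40/37/24 (IPE; mean 186/101 = 1.842): change is 0.158 in each arm, a difference of 0.00.
   - The planned test gives p = 0.083 in both cases.

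**Precision.** Simulations compared the planned test with a proportional odds model adjusted for baseline category. All used 101 per arm, a latent shift of 0.4 SD and baseline correlations of 0.4, 0.5 and 0.6, all assumed.

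| Assumed category shares | Runs | Planned test | Adjusted model | Gain (points) |
|---|---|---|---|---|
| 35/40/25 | 1,000 | 74%, 73%, 73% | 78%, 80%, 84% | 4, 7, 11 |
| Equal thirds | 500 | 72%, 73%, 71% | 78%, 78%, 81% | 6, 5, 10 |

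The gain is roughly 5 to 10 points. The planned test ignores baseline, so its true power cannot depend on the baseline correlation; the variation along its column is simulation noise.

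**The case against.** A reader might infer that the plan contains no measure of change in physical activity. It does: the same row plans change from baseline and cross-tabulations with baseline. What is missing is a between-arm estimate with an interval.

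A reader might also infer that physical activity as a whole gets no effect size. Accelerometry does get a difference with 95% CI, though only in the sub-study, planned at 52 participants. The gap is specific to IPAQ. The planned IPAQ proportions would also let a reader work out a crude 12-month difference and see any baseline difference.

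The clash between sections can be pressed too far. Section 6 speaks of other outcomes and does not forbid further p-values. The effect-size sentence in section 7.10 concerns secondary outcomes, while section 3.6 lists lifestyle factors separately, and section 7.4 opens by promising simple descriptive statistics. One could say that the general CI commitment in section 6 still applies and the table cell merely fails to repeat it. That is fair as far as it goes, but the cell names a method that supplies no interval and leaves open which effect the interval would describe.

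Comparing arms at 12 months is not an error. Section 6 gives the latest timepoint most weight, randomisation makes the comparison valid, and the smoking and drinking rows also compare current status. The linear-by-linear test is a standard choice for ordered categories. What stands against it is the missing estimate and interval, and the unused baseline.

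**Conclusion.** The point holds in a limited form. For IPAQ, change is planned only descriptively, and the only between-arm inference is a valid 12-month test that ignores baseline and gives no estimate or 95% CI. This does not meet the general statement in section 6 and differs from every other row of table 7.4, although an arm difference would prompt sensitivity analyses.

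The conclusion about the missing interval rests on the SAP's wording alone. The illustration (p = 0.083 against an odds ratio of 1.58 with a CI from 0.94 to 2.63) uses assumed counts and shows only the kind of information lost. The power gain from adjustment is secondary: it depends on assumed category shares, shift and baseline correlation, and the SAP sets no power target for IPAQ.

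Severity is low. IPAQ is a supporting lifestyle variable, and the primary analysis of body weight does not depend on it.

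**What to change.** In the IPAQ row of table 7.4, replace or supplement the test with a between-arm effect and 95% CI at 12 months. The preferred choice is an odds ratio from a proportional odds model for 12-month IPAQ category, with arm and baseline IPAQ category as covariates. If proportional odds is doubtful, report the difference in proportion Low with 95% CI, in the style of the smoking and drinking rows. Keep the descriptive change summaries and the cross-tabulations with baseline.

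The cost is one table cell. The data are already collected, and the model is standard in statistical software. The downside is the proportional odds assumption, which can be checked, with the planned cross-tabulations as a starting point. The adjusted odds ratio compares 12-month category given baseline category; it is not itself a change score, and the table should say so.
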